#### 9.3.1. Study Time Periods for Concomitant Medications and Blood and Blood Supportive Care Products

Concomitant Medication and Blood and Blood Supportive Care Product start and end dates will be assigned to study time periods in relation to first dose of study treatment as defined below. The start date references time flag variables and end date reference time

flag variables will be added to the concomitant medications and blood and blood supportive products datasets, respectively.

- **Start relative to treatment:** Assign to 'BEFORE' if start date is prior to study treatment start date or if subject has not taken any study treatment or (start date is missing and end date is before study treatment start date). Else assign to 'DURING' if the start date falls into the on-therapy period as defined above or if subject is ongoing (not all study treatment discontinuation records completed) or start date is missing. Else assign to 'AFTER' if start date is after the on-therapy period.
- **End relative to treatment:** Assign to 'BEFORE' if end date is prior to study treatment start date or if subject has not taken any study treatment. Else assign to 'DURING' if start date falls into the on-therapy period or if subject is ongoing (not all study treatment discontinuation records completed) or (end date is missing and start relative to treatment not 'AFTER'). Else assign to 'AFTER' if start date is after the on-therapy period or (end date is missing and start relative to treatment='AFTER').

Only on-therapy blood and blood supportive care products that start after the start of study treatment are included in the Blood Products and Blood Supportive Care Product summaries. Therefore, for summary tables, include blood and blood supportive care product records where start relative to treatment in ('DURING') and end relative to treatment in ('DURING','AFTER'). All data will be reported in listings.

Concomitant medication start relative to treatment and end relative to treatment flags are used to select data to include in the Concomitant Medication summaries as follows:

- **Summary of Concomitant Medications:** This summary will contain medications including those with start date prior to study treatment start date and continue (missing end date or end date after study treatment start date) on therapy. Note that any medications with start date and end date prior to study treatment start date will be excluded. In addition, any medication that was started during post-therapy will be excluded. Include concomitant medication records where start relative to treatment in ('BEFORE','DURING') and end relative to treatment in ('DURING','AFTER').
- **Summary of Concomitant Medications with On-Therapy Onset:** This summary will contain medications with start date after study treatment start date. In addition, any medication that was started during post-therapy (see above for definition of post-therapy) will be excluded. Include concomitant medication records where start relative to treatment in ('DURING') and end relative to treatment in ('DURING','AFTER').

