## 7.1. Data Display Treatment and Other Subgroup Descriptors

For all tabulations, Ofatumumab Maintenance and Observation (no further treatment) will be presented.

All listings will be presented by individual treatment arm.

If the sample size permits, the stratification factors will be used for subgroup analyses. The stratification factors include: CR or PR at study entry; number of previous induction treatments (2 vs 3); and type of prior treatment (chemoimmunotherapy, only alkylating monotherapy, or other treatment).

The following treatment descriptors will be used on all applicable displays:

Treatment Group		Data Display	Order of Treatment Groups
Code	Description		
A	Ofatumumab Maintenance	Ofatumumab	1 st treatment column
B	Observation	Observation	2 nd treatment column

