### 9.3. Study Time Periods

Adverse events, concomitant medications, blood product, death, subject disposition, ECOG, laboratory, image data, vital signs, constitutional symptoms, lymph node examination, organ examination, biomarker, and questionnaire data (EORTC QLQ-C30, EORTC QLQ-CLL16, and EQ-5D) will be assigned to the treatment periods defined below. Flag variables indicating the treatment period will be added to these datasets.

**Pre-therapy** is defined as the time prior to the subject's first dose of study treatment for subjects randomized to the ofatumumab arm. For subjects randomized to the "No further treatment (observation)" arm, pre-therapy is defined as the time prior to the subject's randomization date.

**On-treatment** is defined as the time from start date/time of study treatment until the end date/time of the study treatment + 30 days for subjects randomized to the ofatumumab arm. The start date of the on-treatment phase is the date of the first dose of study drug. The end of study treatment is defined as the last dose of planned treatment. For subjects randomized to the "No further treatment (observation)" arm, on-treatment is defined as the time from randomization until the date of entry into follow-up.

There are specific rules to handle the cases where start date/time is equal to start date/time of study treatment or the start date/time is missing for different classes of data sets:

- For interventions and events, including adverse event, concomitant medications, blood product, death, and disposition, i.e., if the date/time is equal to start date/time of study treatment or time is not available and the date is equal to start date of study treatment, the flag will be set to on-treatment. If the start date is missing, and the end date/time is before start date/time of study treatment, the flag will be set to pretreatment. If start date is missing and end date/time is not before the start date/time of study treatment, or both start date and end date are missing, the flag will be set to on-treatment.

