## 10.5. Concomitant Medications

Concomitant medications will be coded using GSK Drug coding dictionary, summarized, and listed. The summary of concomitant medications will show the number and percentage of subjects taking concomitant medications by Ingredient. Multi-ingredient products will be summarized by their separate ingredients rather than as a combination of ingredients. Anatomical Therapeutic Chemical (ATC) classification Level 1 (Body System) information will be included in the dataset created but will not appear on the listing or summary.

In the summary of concomitant medications, each subject is counted once within each unique ingredient. For example, if a subject takes Amoxicillin on two separate occasions, the subject is counted only once under the ingredient “Amoxicillin”.

Blood products or blood supportive care products with onset date within the on-therapy window will be included in the summary tables. The frequency and percentage of subjects using blood products and blood supportive care products after the start of study medication will be provided. Supporting listings will also be provided.

Concomitant medications will be summarized separately for medications with onset date within the on-therapy period and for medications with onset date within the pre-therapy period. Note: In order to be considered a concomitant medication, the concomitant medication must have been taken at some point during the on-therapy window.

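### As written, SAP 9.3.1 keeps every observation-arm record out of the concomitant-medication and blood-product summaries, and its end flag tests the start date

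*SAP*

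**What the plan says.** SAP 9.3 sets study time periods for data that include concomitant medications and blood products. For the observation arm, "on-treatment is defined as the time from randomization until the date of entry into follow-up". SAP 9.2.1 likewise makes randomization that arm's safety reference date.

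SAP 9.3.1 then defines two flags per record.

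- Start flag: BEFORE "if start date is prior to study treatment start date or if subject has not taken any study treatment". DURING and AFTER follow as Else branches.
- End flag: BEFORE "if end date is prior to study treatment start date or if subject has not taken any study treatment". The next branch assigns DURING "if start date falls into the on-therapy period or if subject is ongoing". The AFTER branch also refers to the start date.

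Three filters use the flags. The blood-product and on-therapy-onset summaries need start = DURING and end = DURING or AFTER. The main concomitant-medication summary needs start = BEFORE or DURING and end = DURING or AFTER. That main summary is described as covering medications with "start date prior to study treatment start date and continue (missing end date or end date after study treatment start date) on therapy".

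SAP 10.5 sets table content by the on-therapy window: "Blood products or blood supportive care products with onset date within the on-therapy window will be included in the summary tables", and to count as concomitant "the concomitant medication must have been taken at some point during the on-therapy window". SAP 7.1 adds: "For all tabulations, Ofatumumab Maintenance and Observation (no further treatment) will be presented".

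**The concern.** The never-dosed clause is the first branch of both flags, and in this trial it describes one whole arm by design. The observation window in 9.3 is mentioned only in later Else branches, which an observation record never reaches. The SAP does not say whether 9.3.1 or 9.3 and 10.5 govern.

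The end flag has a second fault. Its DURING and AFTER branches look at when the medication started, so a medication begun before the first dose and stopped later can match no branch at all.

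Table 1.4240 (concomitant medications) and Table 3.1280 (blood and supportive-care products) are on the output lists of both the 280-event SAP and the final-analysis SAP. Those plans carry the earlier data rules and conventions forward without correcting 9.3.1. Coded literally, both tables could show a structural 0% under observation, and Table 1.4240 could under-count medications carried into the ofatumumab arm. These tables describe supportive care by arm in an open-label trial whose protocol (6.1.8) leaves immunoglobulin, preventive antibiotics and G-CSF to the treating physician.

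**Working it through.** The plan gives no figure to reproduce; the check is of derivation logic. Inputs are the two flag definitions and three filters in 9.3.1, taken in the order written. The on-therapy period of 9.3.1 is read as the on-treatment period of 9.3.

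**Patterns.** Start and end can each be before, on or after the therapy period, or completely missing (SAP 9.2.5 leaves completely missing dates unimputed). With start no later than end there are 4 + 3 + 2 = 9 patterns with a known start and 4 with a missing start, 13 in all. These are logical patterns, not records or subjects.

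**Observation arm.** Start = BEFORE and end = BEFORE for all 13. Every filter needs end = DURING or AFTER, so 0 of 13 are selected in each summary. If only the end-flag slip is corrected, the count is still 0, because the never-dosed clause comes first.

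**Dosed subject, no longer ongoing.** Flags are shown as start/end; 'none' means that no branch applies.

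| Start → end | As written | End date tested | In 1.4240: written / corrected | In 3.1280: written / corrected |
|---|---|---|---|---|
| pre → pre | BEFORE/BEFORE | same | no / no | no / no |
| pre → on | BEFORE/none | BEFORE/DURING | no / yes | no / no |
| pre → post | BEFORE/none | BEFORE/AFTER | no / yes | no / no |
| pre → missing | BEFORE/DURING | same | yes / yes | no / no |
| on → on | DURING/DURING | same | yes / yes | yes / yes |
| on → post | DURING/DURING | DURING/AFTER | yes / yes | yes / yes |
| on → missing | DURING/DURING | same | yes / yes | yes / yes |
| post → post | AFTER/AFTER | same | no / no | no / no |
| post → missing | AFTER/AFTER | same | no / no | no / no |
| missing → pre | BEFORE/BEFORE | same | no / no | no / no |
| missing → on | DURING/none | DURING/DURING | no / yes | no / yes |
| missing → post | DURING/none | DURING/AFTER | no / yes | no / yes |
| missing → missing | DURING/DURING | same | yes / yes | yes / yes |

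- Known start (9): Table 1.4240 has 4 as written against 6 corrected; Table 3.1280 has 3 against 3.
- Missing start (4): 1 against 3 in each.
- Total (13): Table 1.4240 has 4 + 1 = 5 against 6 + 3 = 9; Table 3.1280 has 3 + 1 = 4 against 3 + 3 = 6.
- The on-therapy-onset filter has the same form as the blood-product filter and gives the same counts.

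**Dosed and still ongoing** (8 patterns, no post period). The ongoing clause rescues the end flag: 6 against 6 for Table 1.4240 and 4 against 4 for Table 3.1280.

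**Finer grid.** With day values, an assumed window of days 0 to 700, and both ongoing states, there are 106 combinations. A never-dosed subject has 0 selected in every summary. A dosed subject has 18 with no end flag: 12 with a pre-treatment start and 6 with a missing start. Testing the end date removes all 18. The main summary rises from 73 to 91 (+18) and the other two from 57 to 63 (+6). The never-dosed result does not depend on the assumed window.

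**With both corrections.** Observation patterns match the dosed column: 9 of 13 for Table 1.4240 and 6 of 13 for Table 3.1280.

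**Partial dates.** SAP 9.2.5 sets a start date with the day missing to the 1st of the month when there is no study treatment start date. Take such a record in the randomization month, with the end on, after or missing. Even under corrected flags its start is BEFORE, unless randomization was on the 1st. The blood-product filter then selects 0 of 3, against 3 of 3 for a dosed subject, whose date is set to treatment start. Table 1.4240 still takes the record, since it allows a BEFORE start.

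**The case against.** The strongest reply is that the intent is plain. SAP 9.3 gives the observation arm a window and names these data, 9.2.1 gives it a reference date, and 10.5 sets table content by the on-therapy window. The wording of the end flag reads as a copying slip that the description of the main summary contradicts. SAP 9.2 calls its sections a general description and defers full details to dataset specifications that are not supplied. An all-zero concomitant-medication column would probably be noticed.

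Much of this stands. The intent is recoverable, and nothing shows that the literal rule was run. The conflict with 7.1 is also weak, because a column of zeros still presents the arm. The on-therapy-onset summary is on neither supplied output list. Nothing ties the transfusion summary, Table 3.1210, to these flags; its title covers the whole trial. The pattern counts give no share of records or subjects, and only the observation-arm zero is independent of the grid chosen. Few if any subjects could still have been ongoing at the February 2017 cut-off.

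None of it removes the faults. 9.3.1 is the more specific rule, it is written as executable branches, and its first branch pre-empts the window that 9.3 supplies. The later plans repeat the tables and leave the rule as it is.

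**Conclusion.** The concern holds on the wording, with high confidence. Followed literally, 9.3.1 selects no observation-arm record for any of its three summaries. This assumes that no observation subject was dosed in error; a subject randomized to ofatumumab but never dosed is dropped in the same way.

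The end-flag fault is narrower. It affects dosed subjects who are no longer ongoing. It removes carried-in medications with a known stop on or after treatment start from Table 1.4240. It affects the blood-product summary only where the start date is completely missing.

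The effect on reported results is unknown, because the programs, dataset specifications and interim report are not among the documents. The exposed outputs, Tables 1.4240 and 3.1280, are descriptive. Listings 21.0110 and 23.0300 carry the full data, and PFS does not use these flags. It should be fixed, but it does not threaten the primary result.

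**What to change.** In SAP 9.3.1:

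1. For observation-arm subjects, use the randomization date and the 9.3 observation window in both flags, and define what ongoing means for them.
2. Keep an explicit rule for subjects randomized to ofatumumab but never dosed.
3. Test the end date in the end flag's DURING and AFTER branches.
4. In the SAP 9.2.5 partial-date rule for concomitant medications and blood products, use randomization as the observation arm's reference. Otherwise some blood-product records drop out again after the flags are corrected.

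Then check the programs. Rerun Tables 1.4240 and 3.1280 only where the uncorrected flags were used. Rerun the on-therapy-onset summary and Table 3.1210 only if they were built from these flags.

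The cost is SAP wording, a program check and, if needed, reruns of descriptive tables. No new data are required.

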## **9.4. Values of Potential Clinical Importance**

### **9.4.1. Laboratory Parameters**

Reference ranges for all laboratory parameters collected throughout the study are provided by the laboratory. A laboratory value that is outside the reference range is considered either high abnormal (value above the upper limit of the reference range) or low abnormal (value below the lower limit of the reference range). Note: a high abnormal

or low abnormal laboratory value is not necessarily of clinical concern. The laboratory reference ranges will be provided on the listings of laboratory data. Clinical laboratory test results outside of the reference range will be flagged in the listings.

To identify laboratory values of potential clinical importance, National Cancer Institute Common Terminology Criteria for Adverse Events (NCI-CTCAE v4.0) will be used to assign grades to the relevant laboratory parameters. NCI-CTCAE v4.0 can be found at <http://ctep.cancer.gov/reporting/ctc.html>.

For laboratory data which are not listed in the NCI CTCAE v4.0, a summary of values outside the normal range will be provided.

#### 9.4.2. Vital Signs

To identify heart rate values of potential clinical importance, NCI-CTCAE v4.0 will be used to assign categories that align with the grades for ‘Sinus bradycardia’, ‘Sinus tachycardia’, ‘Supraventricular tachycardia’, and ‘Ventricular tachycardia’.

The following criteria will be used to flag vital sign values that are values of potential clinical importance:

Vital Sign Parameter	Potential Clinical Importance (PCI) Range	Unit
Decrease from baseline Heart Rate	Decrease to <60	bpm
Increase from baseline Heart Rate	Increase to >100	bpm

To identify blood pressure values of potential clinical importance, NCI-CTCAE v4.0 will be used to assign categories that align with the grades for ‘Hypertension’.

Vital Sign Parameter	Potential Clinical Importance (PCI) Range	Unit
Increase from baseline Systolic Blood Pressure	≥120 to <140 (Grade 1) ≥140 to <160 (Grade 2) ≥160 (Grade 3)	mmHg
Increase from baseline Diastolic Blood Pressure	≥80 to <90 (Grade 1) ≥90 to <100 (Grade 2) ≥100 (Grade 3)	mmHg

To identify temperature values of potential clinical importance, NCI-CTCAE v4.0 will be used to assign categories that align with the grades for ‘Hypothermia’ and ‘Fever’.

Vital Sign Parameter	Potential Clinical Importance (PCI) Range	Unit
Increase from baseline temperature	Increase to $\geq 38$	Degrees C
Decrease from baseline Diastolic Blood Pressure	Decrease to $\leq 35$	Degrees C

## 10. STUDY POPULATION

Unless otherwise stated, all tables and listings in this section will be based on the ITT population, and all summaries and data listings will use treatment labels as specified in Section 7].

The list of displays for Study Population is shown in a separate document from the RAP.

The number of subjects enrolled into the study will be summarized by investigator for the ITT population. The total number of subjects in each population specified in Section 6.2 will also be provided.

A listing of subject disposition including investigator and treatment start date will be provided for the ITT population. The number of subjects prematurely discontinuing from the study along with the reason for early study discontinuation will also be summarized and listed.

### 10.1. Disposition of Subjects

A summary of the number of subjects in each of the analysis populations described in Section 6 will be provided. In addition, the number of subjects enrolled by investigator will be summarized by treatment group using the ITT population. A listing of subjects excluded from analysis populations will also be provided.

A summary of subject status and reason for study withdrawal will be provided. This display will show the number and percentage of subjects who withdrew from the study, including primary reasons for study withdrawal. Reasons for study withdrawal will be presented in the order they are displayed in the eCRF.

A summary of study treatment status will be provided. This display will show the number and percentage of subjects who have completed the study, are ongoing, or have discontinued study treatment and a summary of the primary reasons for discontinuation of study treatment. Reasons for study treatment discontinuation will be presented in the order they are displayed in the eCRF. A listing of study treatment discontinuation will be generated. The listing will include last dose date, and reasons for study treatment discontinuation.

## 10.2. Protocol Deviations

All protocol deviations will be summarized and listed and will include inclusion/exclusion deviations as well as other deviations. Protocol deviations will be classified as ‘Deviations that require exclusion from per-protocol population’ and ‘Deviations that do not require exclusion from per-protocol population’.

Subjects who meet the following conditions will be considered as major protocol violators and will be excluded from the per-protocol population:

- Failure to be a PR or CR at study entry
- Received only 1 or more than 3 previous induction treatments
- Failure to demonstrate diagnosis of CLL
- Failure to satisfy the following inclusion criteria: The anti-leukemia treatment before study entry should have been for at least 3 months or 3 cycles.
- Received previous autologous or allogeneic stem cell transplantation (exclusion criteria)
- Had known transformation of CLL (e.g., Richter’s transformation), prolymphocytic leukemia (PLL) or CNS involvement of CLL (exclusion criteria)
- Received prohibited therapies or procedures for CLL

A separate summary and listing of inclusion/exclusion deviations will also be provided.

## 10.3. Demographic and Baseline Characteristics

The demographic characteristics (e.g., age, race, ethnicity, sex, baseline height, and baseline body weight) will be summarized and listed. Age, height and weight will be summarized using the mean, standard deviation, minimum, median, and maximum. In addition, age will also be categorized and summarized for the following categories:

- <18, 18-64, 65-74, and  $\geq 75$
- <70 and  $\geq 70$  years.

The count and percentage will be computed for sex and ethnicity.

Race and racial combinations will be summarized and listed.

The number of subjects enrolled by country and by site will be summarized.

Disease history and characteristics at initial diagnosis (Modified RAI stage, Binet stage) and screening (Modified RAI stage, Binet stage, time since diagnosis (years), and response to last anti-CLL treatment) will be listed. Separate summaries of disease

characteristics at initial diagnosis and screening will be provided. Medical conditions present at screening will be listed and will be summarized along with 12-lead ECG, liver and spleen organ examination, physical lymph node examination, anti-cancer therapies, and concomitant medications.

Prior anti-cancer therapy will be coded using GSK Drug coding dictionary, then summarized by type of therapy and listed. A listing of prior anti-cancer therapy will show the relationship between ATC Level 1, Ingredient, and verbatim text. A summary of the best response to the most recent prior anti-cancer therapy will be provided. A summary of the number of prior anti-cancer therapy regimens will also be produced. A summary of pre-medications required prior to ofatumumab infusion will also be provided

Prior anti-cancer radiotherapy will be summarized and listed. Prior cancer and non-cancer related surgeries will be summarized.

The baseline stratification factors (based on actual data), will be summarized and includes: (1) CR or PR at study entry, (2) number of previous induction treatments and (3) type of prior treatment : chemoimmunotherapy, only alkylating monotherapy, or other treatment.

Summaries of baseline covariates included in Cox proportional hazards model regression analyses (see Section 11) will be provided.

